## 6.2 PECARN Data Coordinating Center (Utah)

In addition to locally secured, identifiable information, partially identifiable information for all sites will be maintained at the PECARN Data Coordinating Center, located at the University of Utah in Salt Lake City, Utah. The Data Coordinating Center has a state-of-the-art computer infrastructure with a dedicated server room with a fire suppression system, air conditioning, cooling system and separate air filtering. The server facility is locked separately from the remainder of the Data Coordinating Center and access to the building is monitored by security personnel year round. The Data Coordinating Center coordinates its network infrastructure and security with the Health Sciences Campus (HSC) information systems at the University of Utah. This provides the Data Coordinating Center with effective firewall hardware, automatic network intrusion detection, and the expertise of dedicated security experts working at the University.

Network equipment includes four high-speed switches. User authentication is centralized with two Windows 2008 domain servers. Communication over public networks is encrypted with virtual point-to-point sessions using SSL or VPN technologies, both of which provide at least 128 bit encryption. OpenClinica (Web-based clinical studies data management system), eRoomTM (Web-based collaborative workspace) and other web applications use the SSL protocol to transmit data securely over the Internet. Direct access to Data Coordinating Center machines is only available while physically located inside the Data Coordinating Center offices, or via a VPN client. All network traffic is monitored for intrusion attempts, security scans are regularly run against our servers, and IT staff are notified of intrusion alerts.

Production servers running mission critical applications are clustered and configured for failover events. Servers are backed up with encryption through a dedicated backup server that connects across an internal 10 gigabit network to a tape drive. Storage area networking (SAN) applications, clusters, and switch-to-switch links are also on a 10 gigabit network. Incremental backups occur hourly during the week. Incremental backups

also are performed nightly with full system backups occurring every week. Tapes are stored in a fireproof safe inside the data center facility, and full backups are taken to an off-site commercial storage facility. Security is maintained with Windows 2008 user/group domain-level security.

Users are required to change their passwords every 90 days, and workstations time out after 5 minutes of inactivity. All files are protected at group and user levels; database security is handled in a similar manner with group level access to databases, tables, and views in Microsoft SQL Server. All portable computers are whole-disk-encrypted.

### **6.3 Data Confidentiality**

The PI and other research personnel have all completed training and received certification in Human Subjects Research Protection and HIPAA. All project staff hired will also successfully complete this training prior to engaging in any research or treatment with study participants and renew this training as required by their institution.

The investigators and staff of the Data Coordinating Center are fully committed to the security and confidentiality of all data collected for PECARN studies. All Data Coordinating Center personnel at the University of Utah have signed confidentiality agreements concerning all data encountered in the center. Violation of these agreements may result in termination from employment at the University of Utah. In addition, all personnel involved with data coordinating center data systems have received Human Subjects Protection and HIPAA education.

The staff, reviewers and investigators involved with this study will be required to sign agreements from the Data Coordinating Center that relate to maintenance of passwords, information system security, and data confidentiality.

### **6.4 Data Quality Management and Monitoring**

The Data Coordinating Center monitors PECARN studies on behalf of the investigators and the funding agency. The purposes of monitoring include demonstration of adherence to human subjects protection requirements and assurance of high quality study data. Monitoring is usually done remotely and may also involve physical site monitoring visits. Site monitoring is described in more detail in Section 9.2.

## 6.5 Record Access

The medical record and study files (including informed consent, permission, and assent documents) must be made available to authorized representatives of the Data Coordinating Center, upon request, for source verification of study documentation. In addition, medical information and data generated by this study must be available for inspection upon request by representatives of the the National Institutes of Health, Food and Drug Administration, and the Institutional Review Board (IRB) for each study site.

## 7 Protection of Human Subjects

### 7.1 Institutional Review Board (IRB) Approval

The Data Coordinating Center and each clinical center must obtain approval from their respective IRB prior to participating in the study. The Data Coordinating Center will track IRB approval status at all participating centers and will not permit subject enrollment without documentation of initial IRB approval and maintenance of that approval throughout subsequent years of the project.

### 7.2 Informed Consent

This protocol requires that parents or other legally empowered guardians sign a parental permission form. The parent or legal guardian will be informed about the objectives of the study and the potential risks. Parents or legal guardians of eligible children with symptoms of gastroenteritis will be approached to provide permission for their child's participation in the study. Parental or guardian permission will be obtained prior to initiation of study activities. Documentation of parental permission will be maintained at the study site. As the maximum eligible age is 48 months, child assent is not applicable.

### 7.3 Potential Risks

Lactobacilli are ubiquitous in the human diet and are a large part of the over 1 trillion live bacteria that reside in the gastrointestinal tract of healthy individuals. Overall, *Lactobacillus rhamnosus* GG, ATCC 53103 (LGG) is well tolerated in the pediatric patient population. Infections (bacteremia, endocarditis, pneumonia, deep abdominal abscesses) have been reported in sick neonates, severely debilitated and immune-compromised individuals given probiotics. The use of probiotics in these individuals continues to be controversial; however prospective studies have been conducted in adults and children

with HIV as well as preterm neonates, with no reported systemic infections. Finally, there are 7 case reports of invasive disease after administration of *Lactobacillus rhamnosus* GG, ATCC 53103 (LGG). These occurred in patients in intensive care units, in patients with central venous catheters, or in patients who are on immunosuppressive therapy, have short gut syndrome, or are at risk for endocarditis. These risk factors are exclusion criteria from our study population.

The clinical risks of invasive infection from *Lactobacillus rhamnosus* are related to receiving *Lactobacillus rhamnosus* GG, ATCC 53103 (LGG). There are risks associated with acute gastroenteritis that are not related to study participation, including dehydration, electrolyte abnormalities, systemic infection and co-infection, and hospital admission. All subjects will be clinically treated for acute gastroenteritis in accordance with local site treatment protocols. There may be other unknown risks of *Lactobacillus rhamnosus* GG, ATCC 53103 (LGG) in children with acute gastroenteritis.

Loss of confidentiality is always a risk in a study, but safeguards are in place to protect against this.

## 7.4 Protections Against Potential Risks

Several steps will be taken to minimize the risks of participation in the study. All of the participating clinical centers are tertiary pediatric hospitals with highly trained pediatric staff. Subjects will be closely followed after discharge. Families will be contacted daily until both the diarrhea and vomiting have resolved and the treatment has been completed. Additional contact will be made on day 14, and months 1, 3, 6, 9 and 12 for long term safety outcomes. Parents or legally authorized representatives will also receive specific instructions as to when to see a health care provider. If an adverse event is reported at the time of follow-up, research personnel will refer subjects for appropriate medical care, when applicable.

Loss of confidentiality will be mitigated by the use of the PECARN Data Coordinating Center which has a highly secure IT infrastructure, and by the existence of trained research staff at participating sites. Data security is described in Section 6.

## 7.5 Potential Benefits

Subjects participating in the study may benefit directly by experiencing less severe disease, shorter duration of symptoms, and decreased need for further health care utilization.

There may also be reduced symptoms (i.e. diarrhea, vomiting, fever) and morbidity, thereby diminishing acute gastroenteritis-associated resource consumption (e.g. physician visits, hospitalization) and societal costs. Additional benefits in the study include closer monitoring of symptoms and potentially earlier recognition of any worsening of acute gastroenteritis due to the frequency of telephone follow up and communication with the family. The knowledge gained in this study may lead to improved treatment options for gastroenteritis for other children and lead to new therapeutic options for future patients. Subjects and their families may therefore benefit indirectly by participating in research with the potential to provide subsequent benefit to others. Finally, future analysis of bulk stool specimens will enable a better understanding of potential mechanisms of action of *Lactobacillus rhamnosus* GG, ATCC 53103 (LGG), which will likely provide benefit to future patients.

## 8 Data and Safety Monitoring Plan

### 8.1 Data Safety Monitoring Board (DSMB)

This study will have a Data Safety Monitoring Board (DSMB) appointed in accordance with instructions from the NICHD program officer. The DSMB will have a charter, will approve the protocol prior to implementation, and will review interim analyses for safety and efficacy.

The purpose of the DSMB is to advise the Federal funding agency (NICHD), the study Principal Investigator ([name]), and the PECARN Steering Committee regarding the continuing safety of study subjects and the continuing validity and scientific merit of the study. The DSMB is responsible for monitoring accrual of study subjects, adherence to the study protocol, assessments of data quality, performance of individual clinical sites, review of serious adverse events and other subject safety issues, and review of formal interim statistical analyses of treatment efficacy.

The Data Coordinating Center will send reports relating to these topics to DSMB members prior to each DSMB meeting. The Data Coordinating Center will staff DSMB meetings. The production and approval of DSMB minutes will be done in accordance with requirements of the NICHD. Each DSMB meeting will have a summary recommendation that will be provided to each participating clinical site for submission to the local Institutional Review Board (IRB). More detailed information from the DSMB meetings will not be routinely provided for local IRB submission.

## 8.2 Frequency of Interim Analysis:

The Data Safety Monitoring Board (DSMB) will meet after 80 patients (safety end points for 1 month), approximately 350 patients (end of 2nd year of enrollment) and 620 patients (end of 3rd year of enrollment) to review enrollment, study procedures, loss to follow-up, drop-in rate, and interim safety and efficacy results. The analyses will test the hypothesis that the probability of developing moderate-to-severe acute gastroenteritis in the probiotic arm is equal to that in the placebo arm. An analysis will also be conducted after 20 subjects under 6 months of age have been enrolled. The DSMB is to review interim data and make recommendations regarding continuation or modification of the study based on safety in this age group. Conservative O'Brien-Fleming monitoring boundaries, implemented using the Lan-DeMets  $\alpha$ -spending function approach, will be used as guidelines for early stopping for efficacy.

## 8.3 Adverse Event Reporting

### 8.3.1 Definitions, Relatedness, Severity and Expectedness

**Definition:** An adverse event (AE) is any untoward medical occurrence experienced by a subject. An event constitutes a disease, a set of related signs or symptoms, or a single sign or symptom. On each study day, the site investigators will evaluate adverse events. Study staff will obtain information on symptoms and adverse events on scheduled follow up calls. Adverse events not previously documented in the study will be recorded on the adverse event record form. The nature of each experience, date and time (where appropriate) of onset, outcome, course, and relationship to treatment should be established.

**Side Effects:** Occurrence of side effects such as weakness, bloating, gas, intestinal rumbling, diarrhea, blood in stool, abdominal pain, abdominal cramps, nausea, vomiting, loss of appetite, heartburn, constipation, skin rash, fever, nasal congestion, sore throat, cough, headache, muscle aches, chills, and diaper rash. Study staff will obtain information about side effects on scheduled follow up contacts.

**Relatedness:** The suspected relationship between study interventions and any adverse event will be determined by the site investigator using the following criteria. *Relatedness may **not** be assessed by a research coordinator, and must be assessed by an investigator.*

**Not Related:** The event is clearly related to other factors, such as the subject's clinical state, therapeutic interventions, or concomitant drugs administered to the subject.

**Possibly Related:** The event follows compatible temporal sequence from the time of beginning the assigned study intervention, but could have been produced by other factors such as the subject's clinical state, therapeutic interventions, or concomitant drugs administered to the subject.

**Probably Related:** The event follows a reasonable temporal sequence from the time of beginning the assigned study intervention, and *cannot be reasonably explained* by other factors such as the subject's clinical state, therapeutic interventions, or concomitant drugs administered to the subject.

Some toxicities will be difficult to distinguish from abdominal symptoms related to acute gastroenteritis (such as bloating, abdominal pain, diarrhea, fever and diaper rash), and only at the time of analysis will we be able to determine whether these signs and symptoms are different between the groups.

**Seriousness:** The severity of clinical adverse events and laboratory abnormalities will be recorded by the site investigator and categorized. A serious adverse event (SAE) is an adverse event that:

- results in death; or
- is life-threatening (the patient was, in the view of the site investigator, in immediate danger of death from the event as it occurred); or
- requires inpatient hospitalization or prolongs an existing hospitalization; or
- results in persistent or significant disability or incapacity; or
- results in congenital anomaly/birth defect; or
- any other event that, based upon appropriate medical judgment, may jeopardize the subject's health and may require medical or surgical intervention to prevent one of the other outcomes listed in this definition.

**Expectedness of the Event:** All adverse events, including serious adverse events, will be evaluated as to whether their occurrence was expected or unexpected. An adverse event is considered expected if it is known to be associated with acute gastroenteritis (acute gastroenteritis), other underlying medical conditions of the subject, is directly related to study outcome, or is otherwise mentioned in the protocol, informed consent, investigator brochure, or other study documents. Expected complications of acute gastroenteritis include abnormal taste, malaise, abdominal distention, foul smelling stools, dehydration, electrolyte and other laboratory abnormalities, other symptoms associated with viral syndromes, systemic infection and co-infection, seizures, and hospital admission.

**Treatment or Action Taken:** For each adverse event, the site investigator will record whether an intervention was required:

- Intervention: Surgery or procedure
- Other Treatment: Medication initiation, change, or discontinuation
- None: No action taken

**Outcome of Event:** Finally, the site investigator will record the clinical outcome of each adverse event as follows:

- Death
- Recovered and the patient returned to baseline status
- Recovered with permanent sequelae
- Symptoms continue

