## 1.3 Trial Endpoints

### Primary Endpoints

- The **primary efficacy endpoint** of this study is the presence of moderate-severe acute gastroenteritis, as defined by a total post-enrollment Modified Vesikari Score  $\geq 9$  during the 2-week follow-up period.
- The **primary safety endpoint** of this study is the occurrence of invasive disease (including meningitis and bacteremia) from *Lactobacillus rhamnosus*.

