#### **8.3.4 Unanticipated Problems (UP)**

Unanticipated problems (UP) are defined as incidents, experiences, or outcomes that are unexpected, related to participation in the study, and suggest that the research places subjects at a greater risk of harm than was previously known or recognized. The site investigator will report unanticipated problems to the Data Coordinating Center within 24 hours. A detailed completed report will be required to be sent to the Data Coordinating Center within 3 working days of the event. After receipt of the complete report, the Data Coordinating Center will report these unanticipated problems to the NICHD Program Official or Project Officer in an expedited manner (within 24 hours). In accordance with local IRB requirements, the site investigator may be required to report such unanticipated problems to the IRB in addition to notifying the Data Coordinating Center. In the event that the medical monitor believes that such an event warrants emergent suspension of enrollment in the trial, and NICHD staff cannot be reached expeditiously, the Data Coordinating Center will notify the study investigator ([name]) and all site investigators to cease enrollment in the trial. Resumption of enrollment will not occur without consent of the NICHD staff after discussion with the DSMB.

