#### **8.3.5 Monitoring Serious Adverse Events**

The Principal Investigator of the Data Coordinating Center ([name]) will act as the medical monitor for this study. If [name] is unavailable, a qualified physician will be designated to fulfill this function. Site investigators and/or research coordinators will report serious adverse events to the Data Coordinating Center within 24 hours. A detailed completed report will be required to be sent to the Data Coordinating Center within 3 working days of the event, and the medical monitor will assess all serious adverse events reported from site investigators.

For each of these serious adverse events, the site investigator will provide sufficient medical history and clinical details for a safety assessment to be made with regard to continuation of the trial. The medical monitor will sign each SAE report after review. All SAE reports will be retained at the Data Coordinating Center, and all SAE reports will be available for review by DSMB members and NICHD staff.

In the unlikely event that the medical monitor believes an unexpected and study-related SAE warrants emergent cessation of enrollment in the trial, NICHD staff and the

DSMB chairperson will be immediately consulted. If these individuals concur with the judgment of the medical monitor, or if the NICHD staff and the DSMB chairperson cannot be reached expeditiously, the Data Coordinating Center will notify the study investigator ([name]) and all site investigators to cease enrollment in the trial. Resumption of enrollment will not occur without consent of the NICHD staff after discussion with the DSMB.

In accordance with local IRB requirements, the site investigator may be required to report such events to the IRB in addition to notifying the Data Coordinating Center.

After notification of the NICHD Program Official or Project Officer, and the DSMB chairperson, of *serious, unexpected, and study-related* adverse events or unanticipated problems (UP), decisions will be made whether to continue the study without change, and whether to convene the entire DSMB for an emergent meeting. If a decision is made to suspend enrollment in the trial, this will be reported to the study investigator ([name]) and all clinical investigators, who will be instructed to report this to their local IRB.

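### Read literally, protocol 8.3.1 classes invasive L. rhamnosus disease, the primary safety endpoint, as expected, so no documented route requires expedited DSMB notice of a case

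*Combined protocol and SAP*

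**What the plan says.** **Expectedness (protocol 8.3.1).** An event is expected if it is known to accompany gastroenteritis or another condition of the child, or if it "is directly related to study outcome, or is otherwise mentioned in the protocol, informed consent, investigator brochure, or other study documents". These grounds are alternatives, so one is enough. A list of expected complications of gastroenteritis follows, ending with "other symptoms associated with viral syndromes, systemic infection and co-infection, seizures, and hospital admission".

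**The endpoint (protocol 1.3 and 5.1; SAP 2.2.2).** The primary safety endpoint "is the occurrence of invasive disease (including meningitis and bacteremia) from" *L. rhamnosus*. The SAP puts it first among the safety outcomes, within its section on study outcomes.

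**Where the event is discussed.** Protocol 4.3 gives suspected invasive infection as the main foreseeable reason for an unblinding request. Protocol 7.3 says "there are 7 case reports of invasive disease after administration of" LGG, attributes them to patients with particular risk factors, and adds: "These risk factors are exclusion criteria from our study population".

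**Escalation.** Protocol 8.3.4 defines unanticipated problems as "incidents, experiences, or outcomes that are unexpected, related to participation in the study", with the further condition that they point to more risk than was known. Protocol 8.3.5 ties the medical monitor's emergent consultation to an SAE that is unexpected and study-related. It also provides that, once the funder and DSMB chairperson are notified of serious, unexpected, study-related events or unanticipated problems, it is decided whether the trial continues unchanged and "whether to convene the entire DSMB for an emergent meeting". Protocol 8.3.6 limits mandatory follow-up of unresolved events to those that are serious, unexpected and related.

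**The concern.** Expectedness decides whether a safety event is escalated or waits. The 8.3.1 definition turns on whether an event has been written down somewhere, not on whether its nature, severity or frequency was foreseen in this population. A primary safety endpoint is always written down, so a definition of this kind makes it expected by construction.

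The event at issue is the one the trial was set up to detect as a harm of the active agent. If it is filed as an expected SAE, nobody is obliged to tell the DSMB before its next scheduled meeting, and enrollment continues meanwhile. No monitoring boundary compensates for this: protocol 8.2 provides boundaries for efficacy only.

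**Working it through.** No statistical figure is involved. The check applies the 8.3.1 rule to the endpoint, follows the result through each reporting route, and then measures the interval between scheduled reviews.

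**Step 1. Classification.**
- Study-outcome clause: the endpoint is a study outcome under protocol 1.3 and in the SAP's own terms (2.2.2), so the clause is met.
- Otherwise-mentioned clause: the event is discussed in protocol 4.3 and 7.3, so the clause is met.
- Exemption for the primary safety endpoint: none found in the protocol or SAP.
- Against this, protocol 7.3 says the risk factors in the known cases are excluded here. By that reasoning a case in an eligible child would be new information. Sections 7.3 and 8.3.1 therefore conflict.

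**Step 2. Routes.**

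| Route | Section | Must the event be unexpected? |
|---|---|---|
| Unanticipated-problem report, with funder notice | 8.3.4 | Yes |
| Monitor's emergent consultation on ceasing enrollment | 8.3.5 | Yes |
| Notice to funder and DSMB chairperson; decision on an emergent meeting | 8.3.5 | Yes |
| Mandatory follow-up of unresolved events | 8.3.6 | Yes |
| SAE report to the coordinating center within 24 hours | 8.3.5 | No |
| Medical monitor assesses and signs every SAE | 8.3.5 | No |
| SAE reports open to DSMB members and funder staff | 8.3.5 | No, but no timed notice |
| Unblinding events | 4.3 | No; next scheduled DSMB meeting |
| DSMB review of all adverse events | 8.3.5 | No; scheduled meetings |
| Further DSMB meetings as needed | SAP 6.1 | No; no trigger stated |

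Every step that obliges someone to alert the DSMB quickly is in the first group. Nothing in the second group is both mandatory and timed with respect to the DSMB.

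**Step 3. Interval between scheduled reviews.** Inputs: meetings at 80, about 350 and 620 children (protocol 8.2), target 970 (protocol 1.4), planned accrual 225 per year (protocol 5.4.1).
- 350 − 80 = 270 children. The first meeting is undated; at the planned rate, 270/225 = 1.2 years.
- 620 − 350 = 270 children. Section 8.2 places these meetings at the ends of years 2 and 3, so 3 − 2 = 1 year.
- 970 − 620 = 350 children with no meeting scheduled in 8.2. With the SAP 6.1 target of 900 it is 900 − 620 = 280.
- Section 8.2 adds an analysis after 20 children under 6 months. It is undated and could shorten one of these intervals.

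**The case against.** **Review is not blocked.** A reader might infer that the endpoint cannot trigger DSMB review, or reaches the DSMB only at a scheduled meeting. The documents do not support that. Under 8.3.5 the coordinating center hears of every SAE within 24 hours and the medical monitor assesses each one. The site must also supply enough detail on each for a safety judgment about continuing the trial, whether or not the event was expected. DSMB members may see the reports, and SAP 6.1 allows extra meetings and analyses. This stands. What remains is that none of it requires expedited notice to the DSMB.

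**Systemic infection is not a further ground.** The list in 8.3.1 that includes it concerns complications of gastroenteritis. Section 7.3 separates infection from the study organism, attributed to receiving LGG, from systemic infection that arises from the illness itself. The point rests on the two broad clauses alone.

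**An investigator might read the rule more narrowly.** Protocol version 1.0 named bacteremia as an expected probiotic reaction and the current text does not. With 7.3, that gives a reasonable basis for calling a case unexpected. It would be wrong to assume that every case will be misclassified. But the outcome then depends on which section the investigator follows.

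**The DSMB charter may contain a notification rule.** Protocol 8.1 mentions a charter, which is not among the documents. If it requires prompt notice, the practical gap closes, though the protocol would still contradict itself.

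**The delay is not 1.2 years throughout.** Dividing 270 by 225 suggests that both gaps between meetings exceed a year, but the protocol's own calendar makes the second exactly one year.

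**Conclusion.** The point holds as a conflict in the safety reporting rules. Taken literally, 8.3.1 makes the primary safety endpoint expected, against the reasoning of 7.3. The expedited steps in 8.3.4 and 8.3.5 and the follow-up duty in 8.3.6 then do not apply to it. The conclusion is that no documented route requires expedited DSMB notice of a case, not that such notice is impossible.

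Any case classified by the literal reading is affected. Without discretionary action, DSMB review could wait while up to 270 children are enrolled between scheduled meetings, or 350 after the last one, subject to the undated infant analysis.

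This assumes that a case would qualify as an SAE, which bacteremia or meningitis ordinarily would, and that the charter adds no notification rule. The documents give no expected rate, so the number of cases is not estimated. Collection of the endpoint is not in question: SAEs are recorded for twelve months after the last dose (8.3.2).

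**What to change.** Reconcile protocol 1.3, 7.3, 8.3.1, 8.3.4, 8.3.5 and 8.3.6 with one or two sentences in 8.3.1:

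- State that the primary safety endpoint as defined in 1.3, invasive disease from *L. rhamnosus*, is not expected for the purposes of 8.3.4 to 8.3.6.
- Limit the study-outcome clause to the efficacy outcomes, and the otherwise-mentioned clause to the complications listed as expected.

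The wording should keep to the endpoint as defined. A trigger on any *Lactobacillus* isolate would be wider than 1.3. If the charter already has a notification rule, 8.3.1 should agree with it.

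This changes classification and notification only. No treatment or stopping rule, data item or efficacy analysis is touched. The cost is the amendment text and an occasional extra notification for an event that should be rare.
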